3 STUDY DESIGN

This is an extension study, to provide continued access to PRO 140 to subjects who complete participation in PRO140_CD02 or CD02_OpenLabel and continue to receive clinical benefit and would require PRO 140 to form a viable regimen, in the opinion of the treating physician. The patient population for this trial is treatment-experienced HIV-infected patients with CCR5-tropic virus who demonstrate evidence of HIV-1 suppression after successfully completed 24 weeks of treatment in the PRO140_CD02 or CD02_Open Label study.

Subjects participating under Protocol versions 1.0-3.0 received 350 mg of PRO 140. Dose was increased from 350 mg to 700 mg weekly to provide maximum viral load suppression in a heavily treatment experienced population to avoid developing resistance to current OBT therapies.

Those that were enrolled under version 1.0-3.0 have the option of remaining on their current dose of 350mg or increasing their dose to 700 mg for the remainder of the trial.

The study is divided into three phases: Screening, Treatment Extension and Follow-up.

Screening Phase begins with signing of Informed Consent and lasts up to 21 days. All subjects will continue taking PRO 140 SC injection in addition to OBT during the Screening Phase.

Subject will enter the Treatment Extension Phase as soon as HIV-1 viral load results are available for review by Investigator. Treatment Extension Phase consists of weekly study treatment injections along with OBT. Study participants will be regularly monitored for viral load and will cease weekly study treatment injections should they experience virologic failure. Virologic failure is defined two consecutive HIV-1 RNA levels ≥ 400 copies/mL.

Note: Subjects will be allowed to continue PRO 140 with existing OBT regimen while waiting for new regimen to be constructed by the Investigator.

Subjects who experience virologic failure at any point during the Treatment Extension Phase will undergo the Virologic Failure (VF) Visit assessments and will be followed up every 4 weeks until viral suppression is achieved (i.e., plasma HIV-1 RNA levels below level of detection) or up to a maximum of 6 months after cessation of therapy if the treating physician does not feel that there is an antiretroviral regimen that will regain full viral suppression. Subjects who do not experience virologic failure, will be followed up every 2 weeks for total of 4 weeks.

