4 STUDY SCHEDULE

This study is divided into three phases: Screening, Treatment and Follow-up.

(1) **Screening Phase:** This phase lasts up to 21 days and begins with signing of Informed Consent. Assessments performed during this phase determine the subject's final eligibility for study participation. Subjects who meet all eligibility criteria will receive first treatment injection at Treatment Extension Visit 1 (*which corresponds to EOT from PRO140_CD02 or CD02_OpenLabel study*).

All subjects will continue taking PRO 140 along with OBT during the Screening Phase.

Note: Subject consent and screening assessments should be completed prior to EOT visit in the PRO140_CD02 or CD02_OpenLabel study.

(2) **Treatment Extension Phase:** Subjects will receive weekly treatments (window period of ± 3 days) until virologic failure is experienced, consent is withdrawn, the study drug is approved, or the trial is completed/ended by CytoDyn, whichever comes first.

Virologic failure is defined as two consecutive HIV-1 RNA levels ≥ 400 copies/mL.

Subjects who meet all eligibility criteria will receive first treatment injection at Treatment Extension Visit 1 (*which corresponds to EOT from PRO140_CD02 or CD02_OpenLabel study*).

PRO 140 will be administered by a qualified medical professional (MD, DO, PA, LPN, LVN, NP, RN, or CMA if permitted by state law) or self-administered by subjects.

Any time during the Treatment Extension Phase, if virologic failure occurs, Investigator will readjust antiretroviral regimen based on HIV-1 genotypic and/or phenotypic drug resistance results obtained during the VF visit.

Subjects will be allowed to continue PRO 140 with existing OBT regimen while waiting for new regimen to be constructed by the Investigator.

(3) **Follow-Up Phase:** The duration of follow-up depends on whether or not subject has experienced virologic failure during the Treatment Extension Phase.

- Subjects who experience virologic failure within Treatment Extension Phase will be followed up every 4 weeks until viral suppression is achieved (i.e., plasma HIV-1 RNA levels below level of detection) or up to a maximum of 6 months after cessation of therapy if the treating physician does not feel that there is an antiretroviral regimen that will regain full viral suppression.
- Subjects who do not experience virologic failure at the end of Treatment Extension Phase, will be followed up every 2 weeks for total of 4 weeks.

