- [6] Hemoglobin, Hematocrit (HCT), Red Blood Cells (RBC), White Blood Cells (WBC) with total and differential count, Absolute Neutrophil Count (ANC) and platelets.
- [7] Serum Biochemistry
 - Hepatic function indicators: total and direct bilirubin, alkaline phosphatase, aspartate aminotransferase (AST), alanine aminotransferase (ALT), total protein, Lactate dehydrogenase (LDH)
 - Renal function indicators: BUN, creatinine
 - Electrolytes: sodium, potassium, chloride, calcium and bicarbonate
 - Other: glucose (random), cholesterol (total)
- [8] Prothrombin time (PT) and International Normalized Ratio (INR)
- [9] Urine samples will be tested for color, appearance, specific gravity, pH, protein, glucose, occult blood, ketones, leukocyte esterase, nitrite, bilirubin, urobilinogen, and microscopic examination of urine sediment.
- [10] ONLY performed on women of childbearing potential. Subject will not be allowed to participate if the result is positive.
- [11] Plasma HIV-1 RNA and TruCount T Assay will be performed once every 4 weeks when subject comes to clinic. TruCount T Assay includes: CD3 %, CD4 %, CD8 %, Absolute Lymphocytes, CD3 cell count, CD4 cell count, and CD8 cell count
- [12] Injection Site Reaction will be assessed by the Investigator whenever IP administered at the clinic.
- [13] Monogram Biosciences Trofile® RNA and PhenoSense® Entry Assays [AMD3100 (CXCR4 inhibitor drug), Maraviroc and PRO 140 (CCR5 inhibitor drugs)]
- [14] Monogram Biosciences PhenoSense® GT Assay
- [15] Every 12 weeks during Treatment Extension.
- [16] Refer to [Section 7.11.10](#).

Table 4-2: Schedule of Assessments –Follow-Up (FU) Phase
(a) Subjects who do NOT experience virologic failure

Procedure/Assessments	Follow-Up Visit -1	Follow-Up Visit -2
	NVF-EFU1	NVF-EFU2
Window Period	2 weeks (±3 days) after EOT2 visit	4 weeks (±3 days) after EOT2 visit
Physical Examination	X ^[1]	X ^[1]
Vital Signs	X	X
Plasma HIV-1 RNA level	X	X
TruCount T assay	X	X
Adverse Events	X	X
Concomitant Medications	X	X

[1] Symptom-directed physical examination

(b) Subjects who experience virologic failure

Procedure/Assessments	Follow-Up Visit -1	Follow-Up Visit -2	Follow-Up Visit -3 ^[1]
	VF-EFU1	VF-EFU2	VF-EFU3
Window Period	4 weeks (±7 days) after VF visit	8 weeks (±7 days) after VF	12 weeks (±7 days) after VF
Physical Examination	X ^[2]	X ^[2]	X ^[2]
Vital Signs	X	X	X
Plasma HIV-1 RNA level	X	X	X
TruCount T assay	X	X	X
Adverse Events	X	X	X
Concomitant Medications	X	X	X

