4.2 TREATMENT EXTENSION PHASE

Treatment Extension Phase begins with an evaluation of viral load–results collected during the Screening Phase. Subjects who meet all eligibility criteria, as per data gathered from Screening

Phase are to be treated. All subjects who fail to meet eligibility criteria will be considered screen failure and exit the study without further evaluation.

As shown in [Table 4-3](#), eligible subjects will receive weekly treatment injections (\pm 3 days) until virologic failure or another reason for discontinuation, occurs, whichever occurs first. Eligible subjects will receive PRO 140 700mg* administered as two subcutaneous injections along with Optimized Background Therapy (OBT).

Note: Subjects enrolled prior to Protocol v4.0 may still be receiving the original 350mg dose and have the option of increasing their dose to 700mg.

Table 4-3: Treatment Extension Phase [PRO 140 + OBT]

Study Drug	Dosage Form	IP concentration	Dosing Frequency and Amount	Route of Administration
PRO 140	Parenteral solution	175 mg/mL	2 injections of PRO 140 (2 X 2 mL/inj.) per week	SC injection

The study treatment (PRO 140 SC injections) will be administered by a qualified medical professional (MD, DO, PA, LPN, LVN, NP, RN, or CMA if permitted by state law) or self-administered by subjects depending on the study visit week.

All study subjects will continue their current Optimized Background Therapy:

- Throughout the Treatment Extension Phase, or
- Anytime during the Treatment Extension Phase, if virologic failure occurs or have met any other criteria for discontinuation of study treatment as specified in [section 5.2.1](#) of the protocol. Subjects will be allowed to continue PRO 140 with existing OBT regimen while waiting for new regimen to be constructed by the Investigator.

Note:

- Subjects may return to clinic for an additional blood draw in-between the clinic visits for plasma HIV-1 RNA or CD4+ levels, per the discretion of the Investigator.
- Subjects who experience virologic failure at any time during the Treatment Extension Phase will undergo the Virologic Failure (VF) Visit assessments and enter the Follow-up Phase of the study.
- Subjects who meet any criteria (other than virologic failure) for discontinuation of study treatment as specified in [section 5.2.1](#) of the protocol, will undergo End of Treatment

Extension Phase (EOT2) Visit assessments and enter the Follow-up Phase of the study.

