4.3 FOLLOW-UP PHASE

The duration of follow-up depends on whether subject experiences virologic failure.

- Subjects who experience virologic failure within the Treatment Extension Phase will be followed up every 4 weeks until viral suppression is achieved (i.e., plasma HIV-1 RNA levels below level of detection) or up to a maximum of 6 months after cessation of therapy if the treating physician does not feel that there is an antiretroviral regimen that will regain full viral suppression.
- Subjects who do not experience virologic failure at the end of the Treatment Extension Phase, will be followed up every 2 weeks for total of 4 weeks.

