5 SUBJECT COMPLETION AND WITHDRAWAL

5.1 SUBJECT COMPLETION

- A subject who completes the Treatment Extension Phase (without virologic failure) and 4-week Non-Virologic Failure Follow-Up Phase will be considered as having completed the study.
- A subject who experiences virologic failure during the Treatment Extension Phase, undergoes the Virologic Failure (VF) Visit assessments and is followed up until viral suppression is achieved or up to a maximum of 6 months after experiencing virologic failure if the treating physician does not feel that there is an antiretroviral regimen that will regain full viral suppression will be considered as having completed the study.

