9.1.1 Reporting of Adverse Events

Report initiation for all AEs and SAEs will begin at the time of the first treatment extension visit and continue up until the final study visit (i.e. up to NVF-FU2 for subject who do not experience virologic failure or until viral suppression is achieved for subjects who experience virologic failure). All events will be followed to resolution or until 30 days after the subject completes the study. A final assessment of outcome will be made at that time.

All AEs must be recorded in the subject's medical records and on the eCRFs. AEs will be reported using customary medical terminology along with the following information: the onset and end dates, whether the event is considered to be a SAE (see [Section 9.2](#)), the impact the event had on study treatment (see [Section 9.1.2](#)), the DAIDS AE grade (intensity) of the event (see [Section 9.1.3](#)), the causality of the event (see [Section 9.1.4](#)), whether treatment was given as a result of the event (see [Section 9.1.5](#)), and the outcome of the event (see [Section 9.1.6](#)).

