9.3 REPORTING OF SERIOUS ADVERSE EVENTS

The Investigator is required to report all SAEs that occur during the time period specified in [Section 9.1.1](#). Once the Investigator becomes aware of an SAE, he/she must report the SAE to [REDACTED] within 24 hours:

CRO Medical Monitor	[REDACTED]
	[REDACTED]

The Amarex Medical Monitor may request additional supporting documentation as it becomes available, such as lab reports, ECG reports, discharge summary, hospital notes, etc.

The Investigator is also responsible for reporting all SAEs to the appropriate Institutional Review Board (IRB) in accordance with local laws and regulations. The Investigator is responsible for maintaining documentation in the study file that indicates the IRB has been properly notified. Under 21 CFR 312.32(c), the sponsor is required to notify FDA and all participating investigators in an IND safety report (i.e., 7- or 15-day expedited report) of potentially serious risks from clinical trials or any other source as soon as possible, but no later than 15 calendar days after the sponsor receives the safety information and determines that the information qualifies for reporting. Participating investigators include all investigators to whom the sponsor is providing drug under any of its INDs or under any investigator's IND (21 CFR 312.32(c)(1)).

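### For virologic-failure subjects, new AE/SAE collection ends at viral suppression with no minimum time after the last PRO 140 dose, although dosing may continue past the visit that anchors follow-up

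*Protocol*

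**What the plan says.** Protocol 9.1.1 starts AE and SAE reporting at the first extension visit and runs it to the final study visit. It explains that end point as the second follow-up visit for non-failing subjects, and "until viral suppression is achieved for subjects who experience virologic failure". Section 9.3 adopts the same period for serious events: "The Investigator is required to report all SAEs that occur during the time period specified in" Section 9.1.1.

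Follow-up and completion use the same event. Under Section 4.3, failing subjects "will be followed up every 4 weeks until viral suppression is achieved", with a 6-month maximum if the physician sees no regimen that would restore suppression. Section 5.1 counts as a completer a failing subject who has the VF visit and "is followed up until viral suppression is achieved or up to a maximum of 6 months after experiencing virologic failure", with the same proviso.

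Dosing need not stop at the VF visit. Section 3 notes: "Subjects will be allowed to continue PRO 140 with existing OBT regimen while waiting for new regimen to be constructed by the Investigator". Sections 4, 4.2 and 5.2.1 repeat this, and none sets a limit. The new regimen depends on samples taken at that visit, since the "Investigator will readjust antiretroviral regimen based on HIV-1 genotypic and/or phenotypic drug resistance results obtained during the VF visit" (Section 4). Meanwhile Section 4.2 has failing subjects undergo the "Virologic Failure (VF) Visit assessments and enter the Follow-up Phase of the study". Dosing can therefore overlap with follow-up.

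Table 4-2(b) places the first VF follow-up visit (VF-EFU1) at "4 weeks (±7 days) after VF visit" and the second (VF-EFU2) at 8 weeks ±7 days. Table 4-2(a) places the last visit for non-failing subjects at 4 weeks ±3 days after the end-of-treatment visit, EOT2.

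**The concern.** For a non-failing subject the anchor visit, EOT2, closes the treatment phase, so the last dose is at or before it and the 4-week visit guarantees a post-dose period. For a failing subject the last dose may come after the anchor, and the stopping event is a virological result that has no fixed relation to the last dose. A subject who continues PRO 140 for a time and is then found suppressed can leave the study soon after the last injection. An AE or SAE that starts after that is outside the reporting period.

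The missing days may still be days of drug effect. Protocol 1.4.2.4 reports CCR5 masking for 2-4 weeks after a single intravenous dose, and 1.4.2.5 reports high receptor occupancy for 29 days. Serum half-life was shorter, at 3.5-3.9 days, and the documents give no matching figure for 700 mg subcutaneously each week. Serious events and Grade 3 or 4 events are named study measures (Section 8.2), so completeness of collection matters even in a descriptive study.

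**Working it through.** The plan gives no figure of its own to reproduce. The check is arithmetic on the visit windows.

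**Inputs**
- Last non-failing visit (Table 4-2(a)): 28 ± 3 = 25-31 days after EOT2.
- VF-EFU1 (Table 4-2(b)): 28 ± 7 = 21-35 days after the VF visit.
- VF-EFU2 (Table 4-2(b)): 56 ± 7 = 49-63 days after the VF visit.
- *b* = days from the VF visit to the last PRO 140 dose. The documents set no cap, so *b* is an assumption shown as a range.

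**Formula.** Post-dose days = day of the closing visit − *b*. The comparator is the non-failing minimum of 25 days, taking the last dose at EOT2. An earlier last dose would lengthen the comparator.

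| *b* | Closing at VF-EFU1: (21−*b*) to (35−*b*) | Closing at VF-EFU2: (49−*b*) to (63−*b*) |
|---|---|---|
| 0 | 21-35 | 49-63 |
| 7 | 14-28 | 42-56 |
| 14 | 7-21 | 35-49 |
| 21 | 0-14 | 28-42 |

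**Thresholds**
- Closing at VF-EFU1, short at any permitted timing: 35 − *b* < 25, so *b* > 10. For *b* from 0 to 10 the result depends on where in its window the visit falls. With both visits on nominal day 28, the shortfall is 28 − (28 − *b*) = *b* days.
- Closing at VF-EFU2, shortfall possible: 49 − *b* < 25, so *b* > 24. Short at any permitted timing: 63 − *b* < 25, so *b* > 38.

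**How fast suppression must come.** If PRO 140 continues only until the new regimen starts, time on that regimen at VF-EFU1 is at most 35 − *b*: 28, 21 and 14 days for *b* = 7, 14 and 21. The last two look unlikely unless the subject re-suppresses on the old regimen.

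**Do other clauses supply a minimum?**
- The 30-day sentence in 9.1.1 and the rule in 9.3.1 follow events already reported. They do not extend collection of new ones.
- Section 5.2.2 has discontinued patients followed per protocol where possible, which leads back to the same stopping rule.
- The 6-month limit is a maximum. Sections 3, 4 and 4.3 count it from stopping therapy; 5.1 and the Table 4-2(b) footnote count it from virologic failure.

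**The case against.** The strongest objection is that VF-EFU2 may always be done. The governing words of 9.1.1 are that reporting runs to the final study visit, and suppression appears only in the explanatory bracket. Table 4-2(b) lists VF-EFU1 and VF-EFU2 without condition and attaches the until-suppression footnote to VF-EFU3 alone. SAP Table 8-2 repeats that layout. On this reading there is no shortfall for *b* = 7, 14 or 21. The objection stands as a reading, but 4.3, 5.1 and 9.1.1 all end follow-up at suppression and none requires VF-EFU2. Because continued dosing has no cap, neither reading guarantees a post-dose minimum.

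The scenario is also narrow. The subject must fail twice at 400 copies/mL or more, stay on PRO 140 for more than 10 days after the VF visit, and be below detection by day 35, in a heavily treatment-experienced population. That stands. AEs during continued dosing are still collected at each VF follow-up visit up to closure, pregnancies are followed to term (5.2), and the sponsor's expedited-reporting duty in 9.3 covers serious risks from any source.

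A reader might infer more than the documents support:
- *Failing subjects generally get less safety follow-up.* Those who are not quickly suppressed are followed longer than non-failing subjects, up to 6 months.
- *A result is biased.* The study is single-arm, the safety analysis is descriptive (Protocol 8.7.5, SAP 7.2.4), and no comparison of failing with non-failing subjects is planned.
- *Harm is being missed.* Receptor occupancy after a single intravenous dose is not evidence of delayed toxicity, and Protocol 1.4.2 reports no pattern of drug-related toxicity.
- *Injection-site checks lapse during continued dosing, because the VF follow-up lists omit them.* Section 6.4 requires examination after each injection, and Table 4-1 footnote 12 requires assessment whenever the product is given at the clinic.

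**Conclusion.** The stopping rule for failing subjects has no minimum time after the last dose, and this holds however VF-EFU2 is read. The size of the gap does depend on that reading. If closure at VF-EFU1 is allowed, the post-dose period is below 25 days at any permitted timing once *b* exceeds 10 days. If VF-EFU2 is always done, a shortfall is possible only beyond 24 days and certain only beyond 38.

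These figures assume that the non-failing subject's last dose is at EOT2 and that visits fall within their stated windows. The documents do not give the duration of continued dosing, assay turnaround or time to suppression, so the number affected among up to 50 subjects cannot be estimated and may be zero. The point is minor: a cheap improvement to safety capture.

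**What to change.** In Protocol 4.3, 5.1, 9.1.1 and Table 4-2(b), end follow-up and new AE/SAE collection for failing subjects at the later of (a) viral suppression, or the 6-month maximum, and (b) 4 weeks (±3 days) after the last PRO 140 dose. Section 9.3 then follows without change, because it refers to 9.1.1. As a clarification only, Table 4-2(b) should also say whether VF-EFU2 is done once a subject is suppressed at VF-EFU1.

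The cost is protocol wording, one table edit, and at most about one extra visit for a few subjects. The existing VF-EFU2 slot usually serves: at its earliest, day 49, it leaves at least 25 post-dose days for any *b* up to 24 (49 − 24 = 25). A subject who stops PRO 140 at the VF visit is unaffected unless VF-EFU1 is done before day 25, when at most 25 − 21 = 4 more days are needed.

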9.1.2 Impact of Study Treatment

The impact the event had on the study treatment will be assessed as either: none, study treatment interrupted, study treatment discontinued, or not applicable. The "not applicable" assessment will be used only when the subject is no longer in the treatment phase of the protocol, or if the outcome of the event was "death".

9.1.3 DAIDS AE Grade (Severity) Assessment

The investigator will carefully evaluate the comments of each subject and the response to treatment in order to judge the true nature and severity of the AE. The question of the relationship of AEs to study drug should be determined by the investigator after thorough consideration of all available facts. To assess severity, the investigator will use the DAIDS AE grading table (for adverse events as well as any injection site reactions refer to [Section 16.2](#) and [Section 16.3](#)).

The general guidelines for assessing the AE grade appear below. Full guidelines may be obtained at http://rsc.tech-res.com/Document/safetyandpharmacovigilance/DAIDS_AE_Grading_Table_v2_NOV2014.

Table 9-1: DAIDS AE Grading Table v2 General Guidelines

Grade	Description
Grade 1	indicates a mild event
Grade 2	indicates a moderate event
Grade 3	indicates a severe event
Grade 4	indicates a potentially life-threatening event
Grade 5	Death related to AE.

DAIDS AE Grading Table Version 2.0- November 2014

9.1.4 Causality Assessment

Adverse events will be assigned a relationship (causality) to the study treatment. The Principal Investigator (PI) must review each AE and make the determination of relationship of the event to the study treatment. Relationship of AEs to study treatment will be classified as follows:

- Definitely related:** This category applies to those AEs that the Investigator feels are incontrovertibly related to the study treatment. An AE may be assigned an attribution of definitely related if or when it meets all of the following criteria: (1) it follows a reasonable temporal sequence from administration of the study treatment; (2) it could not be reasonably explained by the known characteristics of the subject's clinical state, environmental or toxic factors, or other modes of therapy administered to the subject; (3) it follows a known response pattern to treatment with the study treatment.
- Probably related:** This category applies to those AEs which, after careful medical consideration at the time they are evaluated, are felt with a high degree of certainty to be related to the study treatment. An AE may be considered probable if or when (must have three): (1) it follows a reasonable temporal sequence from administration of the study treatment. (2) It could not readily have been produced by subject's clinical state, environmental or toxic factors, or other therapies administered to the subject. (3)

Disappears or is decreased upon discontinuation of the study treatment. (4) It follows a known response pattern to treatment with the study treatment.

3. **Possibly related:** This category applies to those AEs which, after careful medical consideration at the time they are evaluated, are judged unlikely but cannot be ruled out with certainty to the study treatment. An AE may be considered possible if or when (must have two): (1) it follows a reasonable temporal sequence from administration of the study treatment. (2) It could not readily have been produced by subject's clinical state, environmental or toxic factors, or other therapies administered to the subject. (3) Disappears or is decreased upon discontinuation of the study treatment. (4) It follows a known response pattern to treatment with the study treatment.
4. **Remotely related:** In general this category can be considered applicable to those AEs which, after careful medical consideration at the time they are evaluated, are judged likely to be unrelated to the study treatment. An AE may be considered unlikely if or when (must have two): (1) it does not follow a reasonable temporal sequence from administration of the study treatment. (2) It could not readily have been produced by subject's clinical state, environmental or toxic factors, or other therapies administered to the subject. (3) Disappears or is decreased upon discontinuation of the study treatment. (4) It does not follow a known response pattern to treatment with the study treatment.
5. **Unrelated:** This category applies to those AEs which, after careful consideration at the time they are evaluated, are clearly and incontrovertibly due to extraneous causes (disease, environment, etc.) and determined with certainty to have no relationship to the study treatment.

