8.2 DESCRIPTION OF SAFETY MEASURES

The following safety measures will be assessed in this study.

1. Mean change in viral load (HIV-1 RNA levels) at the conclusion of the treatment period
2. Mean change in CD4 cell count at the conclusion of the treatment period
3. Emergence of Dual/Mixed (D/M)- and CXCR4-tropic virus in patients who had exclusive CCR5-tropic virus at study entry.
4. Tolerability of repeated subcutaneous administration of PRO 140 as assessed by investigator-evaluation of injection site reactions
5. Frequency of treatment-related adverse events resulting in study drug discontinuation
6. Frequency of Grade 3 or 4 adverse events as defined by the DAIDS Adverse Event scale
7. Frequency of treatment-emergent serious adverse events

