7.2.4.1 Adverse Events

Adverse events will be classified by system organ class and preferred term (PT) according to the most recent MedDRA dictionary.

Since this is an extension of the PRO 140_CD 02 study, all adverse events (AE) that captured in this study will be considered as Treatment Emergent Adverse Events (TEAEs). The following TEAE summaries will be provided, using frequency counts and percentages:

- Overall (i.e., regardless of severity or relationship to treatment)
- By severity grade (mild, moderate, severe, life threatening or death)
- By relationship to study treatment

In addition, separate summaries of SAEs, and AEs resulting in discontinuation of study treatment will be presented.

Unless otherwise specified, at each level of subject summarization, a subject will be counted only once. If there is more than one occurrence of an event, the event of the worst severity or the worst-case relationship category will be summarized.

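### Two of the four criteria for Remotely related (Protocol 9.1.4) are missing their negation, so a fully related event also qualifies and two weakly related profiles meet no graded category

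*Protocol*

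**What the plan says.** Protocol 9.1.4 has five causality categories. Definitely related needs all of three features: plausible timing, no other reasonable explanation, and a known response pattern. Probably related needs three of four features, the fourth being improvement when treatment stops. Possibly related uses the same four: "An AE may be considered possible if or when (must have two".

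Remotely related is for events that "are judged likely to be unrelated to the study treatment". It too has a count: "An AE may be considered unlikely if or when (must have two". Its item (1) reverses the timing criterion. Item (2) repeats the no-other-ready-cause criterion unchanged. Items (3) and (4) run "3) Disappears or is decreased upon discontinuation of the study treatment. (4) It does not follow a known response pattern", so (3) is unchanged and (4) is reversed.

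Unrelated has no count. It requires that the event be "determined with certainty to have no relationship to the study treatment". The lead-in to Possibly covers events that "are judged unlikely but cannot be ruled out with certainty to the study treatment".

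These categories are used downstream. Protocol 8.2 lists as a study measure "Frequency of treatment-related adverse events resulting in study drug discontinuation", and SAP 2.4 repeats it. Protocol 8.7.5.1 and SAP 7.2.4.1 split treatment-emergent events by attribution (in the SAP, "By relationship to study treatment").

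**The concern.** Having no other ready cause and improving on withdrawal are both evidence for a drug effect. In Remotely related they count towards the opposite conclusion, against the category's own description. Two items reversed and two not looks like a copying slip rather than a choice.

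The slip works in both directions. Strongly related events can satisfy a category meant for probably unrelated ones, and some weakly related events satisfy none. An investigator who counts criteria and one who follows the opening description can place the same event differently.

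The study is single-arm and unblinded, so the relationship split rests on investigator attribution with no comparator rate behind it. Item (3) also concerns what happens after the drug is stopped, which bears directly on the events that the discontinuation outcome counts. Neither document says which categories make an event treatment-related.

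**Working it through.** The plan gives no figure to reproduce here, so the check is a full enumeration.

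**Inputs (all from Protocol 9.1.4).** Score each feature 1 if present and 0 if absent: T = plausible timing, N = no other ready cause, D = improves on discontinuation, P = known response pattern. Let s = T + N + D + P.

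- Definitely: T = N = P = 1
- Probably: s ≥ 3
- Possibly: s ≥ 2
- Remotely as written: r = (1−T) + N + D + (1−P) ≥ 2
- Remotely with (2) and (3) negated: r′ = (1−T) + (1−N) + (1−D) + (1−P) = 4 − s ≥ 2

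**All 16 patterns.**

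| T N D P | s | r (as written) | r′ (negated) | Graded categories met as written |
|---|---|---|---|---|
| 1 1 1 1 | 4 | 2 | 0 | Definitely, Probably, Possibly, Remotely |
| 1 1 1 0 | 3 | 3 | 1 | Probably, Possibly, Remotely |
| 0 1 1 1 | 3 | 3 | 1 | Probably, Possibly, Remotely |
| 1 1 0 1 | 3 | 1 | 1 | Definitely, Probably, Possibly |
| 1 0 1 1 | 3 | 1 | 1 | Probably, Possibly |
| 1 1 0 0 | 2 | 2 | 2 | Possibly, Remotely |
| 1 0 1 0 | 2 | 2 | 2 | Possibly, Remotely |
| 0 1 1 0 | 2 | 4 | 2 | Possibly, Remotely |
| 0 1 0 1 | 2 | 2 | 2 | Possibly, Remotely |
| 0 0 1 1 | 2 | 2 | 2 | Possibly, Remotely |
| 1 0 0 1 | 2 | 0 | 2 | Possibly |
| 0 1 0 0 | 1 | 3 | 3 | Remotely |
| 0 0 1 0 | 1 | 3 | 3 | Remotely |
| 1 0 0 0 | 1 | 1 | 3 | none |
| 0 0 0 1 | 1 | 1 | 3 | none |
| 0 0 0 0 | 0 | 2 | 4 | Remotely |

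**Counts.**

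| | As written | (2) and (3) negated |
|---|---|---|
| s ≥ 3 and also Remotely | 3 of 5 | 0 of 5 |
| s ≤ 1 and no graded category met | 2 of 5 | 0 of 5 |
| Both Possibly and Remotely | 3 + 5 = 8 of 16 | 6 of 16, all with s = 2 |

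The fully related event scores r = 0 + 1 + 1 + 0 = 2 and so meets all four graded categories. The pattern scoring the full 4 on Remotely is 0 1 1 0: no other ready cause and improvement on stopping, without timing or a known pattern.

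**Adding a rule that the highest category met prevails.**

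| | Probably or stronger | Possibly | Remotely | Unplaced |
|---|---|---|---|---|
| Rule, text as written | 5 | 6 | 3 | 2 |
| Rule, plus negation | 5 | 6 | 5 | 0 |

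Negation alone leaves six ties and the rule alone leaves two patterns unplaced. Together they place each pattern once (5 + 6 + 5 = 16).

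**The case against.** The strongest reply is that the counts do not decide the category. The principal investigator makes the determination, the criteria are introduced with *may*, and each category opens with a description of a judgement. No sensible investigator would call a fully related event remote, and the two unplaced patterns could be assigned from the descriptions. This makes gross misassignment unlikely. It does not remove the fault: the counts are worded as requirements, and the descriptions do not separate the two middle categories. The Possibly description and the Remotely criteria sentence both use the word unlikely.

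A second point is fair. Under a highest-category rule, negation changes nothing on the related side (5 and 6 before and after) and only places the two stranded patterns. Among patterns with exactly two features, overlap actually rises from 5 of 6 to 6 of 6. If Possibly and above count as treatment-related, the precedence rule and the definition matter more to the named outcome than the negation does.

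Third, the 16 patterns are not weighted by how often they occur, and improvement on stopping cannot be judged when treatment continues. The counts show what the rule permits and nothing more.

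Last, the consequence is bounded. SAP 7.2.4 plans no inferential statistics, and all events leading to discontinuation are summarised regardless of relationship. The SAP's worst-case convention does not help, because it covers repeat occurrences of an event and not one occurrence that fits two categories.

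**Conclusion.** The concern holds. Items (2) and (3) of Remotely related are wrong as written. By criteria count, 3 of 5 strongly related patterns also qualify as Remotely, and 2 of 16 patterns meet no graded category, with Unrelated open to those two only on certainty. The exposure is inconsistent attribution in the relationship tables and in the outcome on treatment-related discontinuations. It does not reach the total of events leading to discontinuation.

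This assumes that each criterion is scored yes or no, that the counts mean at least two or three, and that the slightly different wording of the other-cause item in Definitely describes the same feature. It should be corrected, but it does not threaten the study.

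**What to change.** 1. In Remotely related, reverse item (2) so that it says the event could readily have arisen from the other causes it already lists, and item (3) so that it says the event does not resolve or lessen when treatment stops.
2. State that the highest category met takes precedence. This settles the six ties that remain after step 1.
3. Reword the Possibly description so that it no longer shares the word unlikely with Remotely.
4. In the SAP, state which categories count as treatment-related, for the discontinuation outcome and the tables.
5. Ask investigators to re-confirm causality for every event that led to study drug discontinuation, whatever category was assigned, so that the re-review is not one-directional. Other events already recorded would keep attributions made under the present text, and a footnote to the relationship table should say so.

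The cost is a few clauses in one short protocol amendment, one SAP sentence and a table footnote, and queries on a small number of event records in at most 50 subjects.
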